14.3.1.2 Unsolicited Adverse Events

Table 124: Serious Adverse Events and All Unsolicited Adverse Events Occurring from Day 1 through Day 365 following the First Vaccination, in Subjects in Any Study Arm by MedDRA System Organ Class and Preferred Term, and by Study Arm – Safety Population

Preferred Term	MedDRA System Organ Class	Group 1 Fluzone (N=X)			Group 2 Fluzone + AF03 (N=X)			Group 3 Fluzone + Advax-CpG (N=X)			Group 4 Flublok (N=X)			Group 5 Flublok + AF03 (N=X)			Group 6 Flublok + Advax-CpG (N=X)			All Subjects (N=X)		
		n	%	Events	n	%	Events	n	%	Events												
Serious Adverse Events																						
All	All	x	x	x	x	x	x	x	x	x	x	x	x	x	x	x	x	x	x	x	x	x
PT1	SOC1	x	x	x	x	x	x	x	x	x	x	x	x	x	x	x	x	x	x	x	x	x
Etc.	Etc.																					
Unsolicited Adverse Events																						
All	All	x	x	x	x	x	x	x	x	x	x	x	x	x	x	x	x	x	x	x	x	x
PT1	SOC1	x	x	x	x	x	x	x	x	x	x	x	x	x	x	x	x	x	x	x	x	x
Etc.	Etc.																					
N = Number of subjects in the Safety Population (number of subjects at risk). n = Number of subjects reporting event. Events = total frequency of events reported. SOC = system organ class PT = preferred term																						

Table with similar format:

Table 125: Serious Adverse Events and All Unsolicited Adverse Events Occurring from Day 1 through Day 29 following the First Vaccination, in Subjects in Any Study Arm by MedDRA System Organ Class and Preferred Term, and by Study Arm – Safety Population

Table 126: Number and Percentage of Subjects Experiencing Unsolicited Adverse Events with 95% Confidence Intervals by MedDRA System Organ Class and Preferred Term, and Study Arm – Safety Population

MedDRA System Organ Class	MedDRA Preferred Term	Group 1 Fluzone (N=X)		Group 2 Fluzone + AF03 (N=X)		Group 3 Fluzone + Advax-CpG (N=X)		Group 4 Flublok (N=X)		Group 5 Flublok + AF03 (N=X)		Group 6 Flublok + Advax-CpG (N=X)	
		n	% (95% CI)	n	% (95% CI)	n	% (95% CI)	n	% (95% CI)	n	% (95% CI)	n	% (95% CI)
Any SOC	Any PT	x	xx (xx-xx)	x	xx (xx-xx)	x	xx (xx-xx)	x	xx (xx-xx)	x	xx (xx-xx)	x	xx (xx-xx)
[SOC 1]	Any PT												
	[PT 1]												
	[PT 2]												
[SOC 2]	Any PT												
	[PT 1]												
	[PT 2]												

N = number of subjects in the Safety Analysis Population. This table presents number and percentage of subjects. A subject is only counted once per PT.

Table with similar format:

Table 127: Number and Percentage of Subjects Experiencing Any Unsolicited Adverse Events from Day 1 through Day 29 with 95% Confidence Intervals by MedDRA System Organ Class and Preferred Term, and Study Arm – Safety Population

Table 128: Number and Percentage of Subjects Experiencing Unsolicited Adverse Events by MedDRA System Organ Class and Preferred Term, Maximum Severity, Relationship, and Study Arm – Safety Population

Study Arm	MedDRA System Organ Class	MedDRA Preferred Term	Any Incidence		Severity ¹						Relationship to Treatment ²			
					Mild		Moderate		Severe		Not Related		Related	
			n	%	n	%	n	%	n	%	n	%	n	%
Group 1: Fluzone (N=X)	Any SOC	Any PT	x	xx	x	xx	x	xx	x	xx	x	xx	x	xx
	[SOC 1]	Any PT												
		[PT 1]												
		[PT 2]												
	[SOC 2]	Any PT												
		[PT 1]												
		[PT 2]												
Group 2: Fluzone + AF03 (N=X)	Any SOC	Any PT	x	xx	x	xx	x	xx	x	xx	x	xx	x	xx
	[SOC 1]	Any PT												
		[PT 1]												
		[PT 2]												
	[SOC 2]	Any PT												
		[PT 1]												
		[PT 2]												
Group 3: Fluzone + Advax-CpG (N=X)	Any SOC	Any PT	x	xx	x	xx	x	xx	x	xx	x	xx	x	xx
	[SOC 1]	Any PT												
		[PT 1]												
		[PT 2]												
	[SOC 2]	Any PT												
		[PT 1]												
		[PT 2]												

Study Arm	MedDRA System Organ Class	MedDRA Preferred Term	Any Incidence		Severity ¹						Relationship to Treatment ²			
					Mild		Moderate		Severe		Not Related		Related	
			n	%	n	%	n	%	n	%	n	%	n	%
Group 4: Flublok (N=X)	Any SOC	Any PT	x	xx	x	xx	x	xx	x	xx	x	xx	x	xx
	[SOC 1]	Any PT												
		[PT 1]												
		[PT 2]												
	[SOC 2]	Any PT												
		[PT 1]												
		[PT 2]												
Group 5: Flublok+ AF03 (N=X)	Any SOC	Any PT	x	xx	x	xx	x	xx	x	xx	x	xx	x	xx
	[SOC 1]	Any PT												
		[PT 1]												
		[PT 2]												
	[SOC 2]	Any PT												
		[PT 1]												
		[PT 2]												
Group 6: Flublok + Advax-CpG (N=X)	Any SOC	Any PT	x	xx	x	xx	x	xx	x	xx	x	xx	x	xx
	[SOC 1]	Any PT												
		[PT 1]												
		[PT 2]												
	[SOC 2]	Any PT												
		[PT 1]												
		[PT 2]												

Note: N = Number of subjects in the Safety Analysis Population.
¹ For severity, a subject is counted once per preferred term and is summarized according to their highest severity.
² For relationship, a subject is only counted once per preferred term and is summarized according to their closest relationship.

Table with similar format:

Table 129: Number and Percentage of Subjects Experiencing Any Unsolicited Adverse Events from Day 1 through Day 29 by MedDRA System Organ Class and Preferred Term, Maximum Severity, Relationship, and Study Arm – Safety Population

Table 130: Number and Percentage of Subjects Experiencing Non-Serious Related Unsolicited Adverse Events by MedDRA System Organ Class and Preferred Term, Maximum Severity, and Study Arm – Safety Population*

Study Arm	MedDRA System Organ Class	MedDRA Preferred Term	Any Incidence		Severity ¹					
					Mild		Moderate		Severe	
			n	%	n	%	n	%	n	%
Group 1: Fluzone (N=X)	Any SOC	Any PT	x	xx	x	xx	x	xx	x	xx
	[SOC 1]	Any PT	x	xx	x	xx	x	xx	x	xx
		[PT 1]								
		[PT 2]								
		[SOC 2]	Any PT							
			[PT 1]							
			[PT 2]							
Group 2: Fluzone + AF03 (N=X)	Any SOC	Any PT	x	xx	x	xx	x	xx	x	xx
	[SOC 1]	Any PT	x	xx	x	xx	x	xx	x	xx
		[PT 1]								
		[PT 2]								
		[SOC 2]	Any PT							
			[PT 1]							
			[PT 2]							
Group 3: Fluzone + Advax-CpG (N=X)	Any SOC	Any PT	x	xx	x	xx	x	xx	x	xx
	[SOC 1]	Any PT	x	xx	x	xx	x	xx	x	xx
		[PT 1]								
		[PT 2]								
		[SOC 2]	Any PT							
			[PT 1]							
			[PT 2]							

Study Arm	MedDRA System Organ Class	MedDRA Preferred Term	Any Incidence		Severity ¹					
					Mild		Moderate		Severe	
			n	%	n	%	n	%	n	%
Group 4: Flublok (N=X)	Any SOC	Any PT	x	xx	x	xx	x	xx	x	xx
	[SOC 1]	Any PT	x	xx	x	xx	x	xx	x	xx
		[PT 1]								
		[PT 2]								
		[SOC 2]	Any PT							
			[PT 1]							
		[PT 2]								
Group 5: Flublok+ AF03 (N=X)	Any SOC	Any PT	x	xx	x	xx	x	xx	x	xx
	[SOC 1]	Any PT	x	xx	x	xx	x	xx	x	xx
		[PT 1]								
		[PT 2]								
		[SOC 2]	Any PT							
			[PT 1]							
		[PT 2]								
Group 6: Flublok + Advax-CpG (N=X)	Any SOC	Any PT	x	xx	x	xx	x	xx	x	xx
	[SOC 1]	Any PT	x	xx	x	xx	x	xx	x	xx
		[PT 1]								
		[PT 2]								
		[SOC 2]	Any PT							
			[PT 1]							
		[PT 2]								

Note: N = Number of subjects in the Safety Analysis Population. This table presents number and percentage of subjects.

¹ For severity, a subject is counted once per preferred term and is summarized according to their highest severity.

Table 131: Number and Percentage of Subjects Experiencing Unsolicited Adverse Events Within 28 Days Post First Study Vaccination by MedDRA System Organ Class and Preferred Term, Day Post Vaccination, and Study Arm – Safety Population

MedDRA System Organ Class	MedDRA Preferred Term	Day 1-8 Post Vac 1		Day 9-29 Post Vac 1		Day 1-29 Post Vac 1	
		n	%	n	%	n	%
Group 1: Fluzone (N=X)							
Any SOC	Any PT	x	xx	x	xx	x	xx
[SOC 1]	Any PT	x	xx	x	xx	x	xx
	[PT 1]	x	xx	x	xx	x	xx
	[PT 2]	x	xx	x	xx	x	xx
[SOC 2]	Any PT	x	xx	x	xx	x	xx
	[PT 1]	x	xx	x	xx	x	xx
	[PT 2]	x	xx	x	xx	x	xx
Group 2: Fluzone + AF03 (N=X)							
Any SOC	Any PT	x	xx	x	xx	x	xx
[SOC 1]	Any PT	x	xx	x	xx	x	xx
	[PT 1]	x	xx	x	xx	x	xx
	[PT 2]	x	xx	x	xx	x	xx
[SOC 2]	Any PT	x	xx	x	xx	x	xx
	[PT 1]	x	xx	x	xx	x	xx
	[PT 2]	x	xx	x	xx	x	xx
Group 3: Fluzone + Advax-CpG (N=X)							
Any SOC	Any PT	x	xx	x	xx	x	xx
[SOC 1]	Any PT	x	xx	x	xx	x	xx
	[PT 1]	x	xx	x	xx	x	xx
	[PT 2]	x	xx	x	xx	x	xx
[SOC 2]	Any PT	x	xx	x	xx	x	xx
	[PT 1]	x	xx	x	xx	x	xx
	[PT 2]	x	xx	x	xx	x	xx

MedDRA System Organ Class	MedDRA Preferred Term	Day 1-8 Post Vac 1		Day 9-29 Post Vac 1		Day 1-29 Post Vac 1	
		n	%	n	%	n	%
Group 4: Flublok (N=X)							
Any SOC	Any PT	x	xx	x	xx	x	xx
[SOC 1]	Any PT	x	xx	x	xx	x	xx
	[PT 1]	x	xx	x	xx	x	xx
	[PT 2]	x	xx	x	xx	x	xx
[SOC 2]	Any PT	x	xx	x	xx	x	xx
	[PT 1]	x	xx	x	xx	x	xx
	[PT 2]	x	xx	x	xx	x	xx
Group 5: Flublok + AF03 (N=X)							
Any SOC	Any PT	x	xx	x	xx	x	xx
[SOC 1]	Any PT	x	xx	x	xx	x	xx
	[PT 1]	x	xx	x	xx	x	xx
	[PT 2]	x	xx	x	xx	x	xx
[SOC 2]	Any PT	x	xx	x	xx	x	xx
	[PT 1]	x	xx	x	xx	x	xx
	[PT 2]	x	xx	x	xx	x	xx
Group 6: Flublok + Advax-CpG (N=X)							
Any SOC	Any PT	x	xx	x	xx	x	xx
[SOC 1]	Any PT	x	xx	x	xx	x	xx
	[PT 1]	x	xx	x	xx	x	xx
	[PT 2]	x	xx	x	xx	x	xx
[SOC 2]	Any PT	x	xx	x	xx	x	xx
	[PT 1]	x	xx	x	xx	x	xx
	[PT 2]	x	xx	x	xx	x	xx
N = Number of subjects in the Safety Analysis Population. This table presents number and percentage of subjects. For each time period, a subject is only counted once per PT.							

Table 132: Number and Percentage of Subjects Experiencing Non-Serious, Related Unsolicited Adverse Events Within 28 Days Post First Study Vaccination by MedDRA System Organ Class and Preferred Term, Day Post Vaccination and Study Arm – Safety Population

MedDRA System Organ Class	MedDRA Preferred Term	Day 1-8 Post Vac 1		Day 9-29 Post Vac 1		Day 1-29 Post Vac 1	
		n	%	n	%	n	%
Group 1: Fluzone (N=X)							
Any SOC	Any PT	x	xx	x	xx	x	xx
[SOC 1]	Any PT	x	xx	x	xx	x	xx
	[PT 1]	x	xx	x	xx	x	xx
	[PT 2]	x	xx	x	xx	x	xx
[SOC 2]	Any PT	x	xx	x	xx	x	xx
	[PT 1]	x	xx	x	xx	x	xx
	[PT 2]	x	xx	x	xx	x	xx
Group 2: Fluzone + AF03 (N=X)							
Any SOC	Any PT	x	xx	x	xx	x	xx
[SOC 1]	Any PT	x	xx	x	xx	x	xx
	[PT 1]	x	xx	x	xx	x	xx
	[PT 2]	x	xx	x	xx	x	xx
[SOC 2]	Any PT	x	xx	x	xx	x	xx
	[PT 1]	x	xx	x	xx	x	xx
	[PT 2]	x	xx	x	xx	x	xx
Group 3: Fluzone + Advax-CpG (N=X)							
Any SOC	Any PT	x	xx	x	xx	x	xx
[SOC 1]	Any PT	x	xx	x	xx	x	xx
	[PT 1]	x	xx	x	xx	x	xx
	[PT 2]	x	xx	x	xx	x	xx
[SOC 2]	Any PT	x	xx	x	xx	x	xx
	[PT 1]	x	xx	x	xx	x	xx
	[PT 2]	x	xx	x	xx	x	xx

MedDRA System Organ Class	MedDRA Preferred Term	Day 1-8 Post Vac 1		Day 9-29 Post Vac 1		Day 1-29 Post Vac 1	
		n	%	n	%	n	%
Group 4: Flublok (N=X)							
Any SOC	Any PT	x	xx	x	xx	x	xx
[SOC 1]	Any PT	x	xx	x	xx	x	xx
	[PT 1]	x	xx	x	xx	x	xx
	[PT 2]	x	xx	x	xx	x	xx
[SOC 2]	Any PT	x	xx	x	xx	x	xx
	[PT 1]	x	xx	x	xx	x	xx
	[PT 2]	x	xx	x	xx	x	xx
Group 5: Flublok + AF03 (N=X)							
Any SOC	Any PT	x	xx	x	xx	x	xx
[SOC 1]	Any PT	x	xx	x	xx	x	xx
	[PT 1]	x	xx	x	xx	x	xx
	[PT 2]	x	xx	x	xx	x	xx
[SOC 2]	Any PT	x	xx	x	xx	x	xx
	[PT 1]	x	xx	x	xx	x	xx
	[PT 2]	x	xx	x	xx	x	xx
Group 6: Flublok + Advax-CpG (N=X)							
Any SOC	Any PT	x	xx	x	xx	x	xx
[SOC 1]	Any PT	x	xx	x	xx	x	xx
	[PT 1]	x	xx	x	xx	x	xx
	[PT 2]	x	xx	x	xx	x	xx
[SOC 2]	Any PT	x	xx	x	xx	x	xx
	[PT 1]	x	xx	x	xx	x	xx
	[PT 2]	x	xx	x	xx	x	xx

N = Number of subjects in the Safety Analysis Population. This table presents number and percentage of subjects. For each time period, a subject is only counted once per PT.

Table 133: Number of Unsolicited Adverse Events by MedDRA System Organ Class and Preferred Term, Day Post Vaccination, and Study Arm – Safety Population

			Day 1-8 Post Vac 1	Day 9-29 Post Vac 1	Day 1-29 Post Vac 1
Study Arm	MedDRA System Organ Class	MedDRA Preferred Term	# of Events	# of Events	# of Events
Group 1: Fluzone (N=X)	Any SOC	Any PT	x	x	x
	[SOC 1]	Any PT			
		[PT 1]			
		[PT 2]			
	[SOC 2]	Any PT			
		[PT 1]			
		[PT 2]			
Group 2: Fluzone + AF03 (N=X)	Any SOC	Any PT	x	x	x
	[SOC 1]	Any PT			
		[PT 1]			
		[PT 2]			
	[SOC 2]	Any PT			
		[PT 1]			
		[PT 2]			
Group 3: Fluzone + Advax-CpG (N=X)	Any SOC	Any PT	x	x	x
	[SOC 1]	Any PT			
		[PT 1]			
		[PT 2]			
	[SOC 2]	Any PT			
		[PT 1]			
		[PT 2]			

			Day 1-8 Post Vac 1	Day 9-29 Post Vac 1	Day 1-29 Post Vac 1
Group 4: Flublok (N=X)	Any SOC	Any PT	x	x	x
	[SOC 1]	Any PT			
		[PT 1]			
		[PT 2]			
	[SOC 2]	Any PT			
		[PT 1]			
		[PT 2]			
Group 5: Flublok+ AF03 (N=X)	Any SOC	Any PT	x	x	x
	[SOC 1]	Any PT			
		[PT 1]			
		[PT 2]			
	[SOC 2]	Any PT			
		[PT 1]			
		[PT 2]			
Group 6: Flublok + Advax-CpG (N=X)	Any SOC	Any PT	x	x	x
	[SOC 1]	Any PT			
		[PT 1]			
		[PT 2]			
	[SOC 2]	Any PT			
		[PT 1]			
		[PT 2]			

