3. STUDY OBJECTIVES AND ENDPOINTS

3.1. Study Objectives and Outcome Measures

Primary Safety Objectives	Primary Safety Outcome Measures

 To assess the safety and reactogenicity of 2018/2019 Fluzone and Flublok with and without AF03 or Advax-CpG55.2 adjuvant. 	
 Occurrence of solicited injection site and systemic reactogenicity events through approximately Day 8 after the first study vaccination. Occurrence of unsolicited adverse events from the time of the first study vaccination through approximately Day 29. Occurrence of all SAEs through approximately 12 months following receipt of the first study vaccination. Occurrence of abnormal clinical safety laboratory AEs from the time of study vaccination through approximately Day 8 after the first study vaccination.
Primary Immunogenicity Objectives	Primary Immunogenicity Outcome Measures

 To assess the serum hemagglutination inhibition (HAI) antibody responses against 2018/2019 QIV strains from baseline (Day 1) to approximately Day 29 after receipt of 2018/2019 Fluzone and Flublok with and without AF03 or Advax-CpG55.2 adjuvant. 	
 The percentage of subjects achieving HAI titer seroconversion against the 2018/2019 QIV strains (defined as either a pre-vaccination titer <1:10 and a post-vaccination titer \geq1:40 or a pre-vaccination titer \geq1:10 and a minimum four-fold rise in post-vaccination antibody titer) on approximately Day 29 for each study group. The percentage of subjects with an HAI titer \geq1:40 against the 2018/2019 QIV strains at baseline and approximately Day 29 for each study group. Geometric mean titers (GMTs) of serum HAI against the 2018/2019 QIV strains at baseline and approximately Day 29 for each study group.

	
 • Ratio of GMTs of serum HAI against the 2018/2019 QIV strains between adjuvanted and unadjuvanted study groups at baseline and approximately Day 29. • Geometric mean fold rise (GMFR) in HAI titers from baseline (Day 1) against the 2018/2019 QIV strains at approximately Day 29 for each study group

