6.2. Timing of Analyses

6.2.1. Expedited Report

Clinical, safety, and reactogenicity data through approximately 56 days after study vaccination will represent the interim clinical database for this trial. Once the last subject completes the visit that occurs approximately 56 days after first study vaccination, the interim clinical database will be cleaned, monitored, and locked. Upon receipt of immunogenicity data for Day 1 and Day 29 (HAI, NAI, and Neut against 2018/2019 QIV strains and heterologous strains) and safety data through Day 57, the sponsor will authorize the SDCC to transfer to Sanofi Pasteur a copy of this unblinded data set. An Expedited Report containing analyses of safety data through Day 57 and HAI, NAI, and Neut data for 2018/2019 QIV strains from baseline (Day 1) and Day 29 unblinded by study arm only will be prepared by the SDCC. These analyses may be made available to the sponsor and pharmaceutical partners for planning subsequent trials as well as to the DSMB for review.

The analyses performed for the Expedited Report or using the data set provided to Sanofi Pasteur will not be used to make any decisions concerning the conduct of this trial. As it is anticipated that subjects will remain in long term safety follow-up at the time of these analyses, blinded investigators and DMID medical monitors not involved in the analysis, publication, or Expedited Report preparation will be responsible for assessing SAEs and AESIs (including Protocol Specified AESIs, MAAEs, NOCMCs and PIMMCs) until all subjects have completed the final follow-up visit.

Tables to be included in the Expedited Report are indicated with the symbol * in the title in [Appendix 1](#).

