6.6. Interim Analyses and Data Monitoring

Interim analyses will only be used to terminate this trial in the event that unanticipated safety events deemed to be of sufficient concern require such action by the sponsor. These assessments will not be made on the basis of testing a formal statistical hypothesis; therefore, p-value adjustment will not be made to any analyses. A DSMB will be convened by DMID to review study progress and participant, clinical, safety, and reactogenicity and immunogenicity data.

An expedited report of safety data through Day 57 and HAI, NAI, and Neut data against 2018/2019 QIV strains and heterologous strains from baseline (Day 1) and Day 29 unblinded by study arm will be prepared in Section 6.2.1; though this report will be released while subjects remain in the trial for long-term safety and immunogenicity follow-up, it will be considered the final analysis of these data.

Emergent public health needs may dictate additional interim safety, reactogenicity, and/or immunogenicity analyses be performed on available information at any time during the trial. If this occurs, immunogenicity data will be analyzed as results are available from the central immunogenicity laboratory.

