14.3 Safety Data

14.3.1 Displays of Adverse Events

Table 117: Overall Summary of Adverse Events- Safety Population*[‡]

	Group 1 Fluzone (N=X)		Group 2 Fluzone + AF03 (N=X)		Group 3 Fluzone + Advax-CpG (N=X)		Group 4 Flublok (N=X)		Group 5 Flublok + AF03 (N=X)		Group 6 Flublok + Advax-CpG (N=X)		All Subjects (N=X)	
	n	%	n	%	n	%	n	%	n	%	n	%	n	%
Subjects ^a with														
At least one local solicited adverse event	x	x	x	x	x	x	x	x	x	x	x	x	x	x
At least one grade 3 local solicited adverse event	x	x	x	x	x	x	x	x	x	x	x	x	x	x
At least one systemic solicited adverse event	x	x	x	x	x	x	x	x	x	x	x	x	x	x
At least one grade 3 systemic solicited adverse event	x	x	x	x	x	x	x	x	x	x	x	x	x	x
At least one unsolicited adverse event	x	x	x	x	x	x	x	x	x	x	x	x	x	x
At least one related unsolicited adverse event	x	x	x	x	x	x	x	x	x	x	x	x	x	x
Mild (Grade 1)	x	x	x	x	x	x	x	x	x	x	x	x	x	x
Moderate (Grade 2)	x	x	x	x	x	x	x	x	x	x	x	x	x	x
Severe (Grade 3)	x	x	x	x	x	x	x	x	x	x	x	x	x	x
Not yet assessed														
At least one severe (Grade 3) unsolicited adverse event	x	x	x	x	x	x	x	x	x	x	x	x	x	x
Related	x	x	x	x	x	x	x	x	x	x	x	x	x	x
Unrelated	x	x	x	x	x	x	x	x	x	x	x	x	x	x

	Group 1 Fluzone (N=X)		Group 2 Fluzone + AF03 (N=X)		Group 3 Fluzone + Advax-CpG (N=X)		Group 4 Flublok (N=X)		Group 5 Flublok + AF03 (N=X)		Group 6 Flublok + Advax-CpG (N=X)		All Subjects (N=X)	
	n	%	n	%	n	%	n	%	n	%	n	%	n	%
Subjects ^a with	x	x	x	x	x	x	x	x	x	x	x	x	x	x
At least one serious adverse event ^b	x	x	x	x	x	x	x	x	x	x	x	x	x	x
At least one related, serious adverse event	x	x	x	x	x	x	x	x	x	x	x	x	x	x
At least one adverse event leading to early termination ^c	x	x	x	x	x	x	x	x	x	x	x	x	x	x
At least one medically attended adverse event	x	x	x	x	x	x	x	x	x	x	x	x	x	x
At least one adverse event of special interest	x	x	x	x	x	x	x	x	x	x	x	x	x	x
At least one new onset chronic medical condition	x	x	x	x	x	x	x	x	x	x	x	x	x	x
At least one potentially immune mediated medical condition	x	x	x	x	x	x	x	x	x	x	x	x	x	x
At least one abnormal clinical safety laboratory adverse event	x	x	x	x	x	x	x	x	x	x	x	x	x	x
Mild (Grade 1)	x	x	x	x	x	x	x	x	x	x	x	x	x	x
Moderate (Grade 2)	x	x	x	x	x	x	x	x	x	x	x	x	x	x
Severe (Grade 3)	x	x	x	x	x	x	x	x	x	x	x	x	x	x
N = Number of subjects in the Safety Population														
^a Subjects are counted once for each category regardless of the number of events.														
^b A listing of Serious Adverse Events is included in Tab AE SAE Listing.														
^c As reported on the Adverse Event eCRF.														

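### The only by-term count of unsolicited adverse events marked for the expedited report covers related events only, so it gives no all-causality count by term and arm for this primary safety outcome

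*SAP*

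**What the plan says.** SAP 3.1 defines the outcome without reference to causality: "Occurrence of unsolicited adverse events from the time of the first study vaccination through approximately Day 29".

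SAP 6.2.1 sets the marking rule: "Tables to be included in the Expedited Report are indicated with the symbol * in the title". The report follows the lock of the Day 57 database. It may go to the sponsor and pharmaceutical partners for planning later trials, and to the DSMB. Protocol 9.6.2 ties the second scheduled DSMB data review to it. SAP 6.6 says of the report that "it will be considered the final analysis of these data".

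In SAP Appendix 1 the marked AE and laboratory outputs are:

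- Table 117, "Overall Summary of Adverse Events- Safety Population": subjects per arm with at least one unsolicited AE of any relationship, and Grade 3 events split into related and unrelated.
- Table 122: solicited events by maximum severity.
- Table 130, titled in part "Non-Serious Related Unsolicited Adverse Events by MedDRA System Organ Class and Preferred Term, Maximum Severity, and Study Arm – Safety Population".
- Tables 134 to 138: subject listings of serious AEs, AEs of special interest (AESIs), potentially immune-mediated conditions (PIMMCs), new-onset chronic conditions (NOCMCs), and non-serious moderate or severe unsolicited AEs.
- Table 139: all laboratory parameters by maximum severity.

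The unmarked tables include Table 127, "Number and Percentage of Subjects Experiencing Any Unsolicited Adverse Events from Day 1 through Day 29 with 95% Confidence Intervals", and Table 129, whose title begins "Number and Percentage of Subjects Experiencing Any Unsolicited Adverse Events from Day 1 through Day 29 by MedDRA System Organ Class and Preferred Term". Both match the primary outcome's window and have no relationship filter. Tables 125 and 131 cover the same window and are also unmarked.

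**The concern.** A relationship judgment is made by a blinded physician, one case at a time. Protocol 2.1 says this is the first human use of Advax with CpG55.2, so an unfamiliar reaction has no established profile to judge it against. The randomized comparison does not need that judgment: an excess of one term in one arm is visible from incidence alone. If the only by-term counts in the report are restricted to related events, an excess in a term that physicians tend to call unrelated is harder to see.

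At stake is what the DSMB has in front of it at its second scheduled review, and what the sponsor and partners read when planning later trials.

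**Working it through.** **1. Which marked tables show what.** Every title in SAP Appendix 1, sections 14.3.1 and 14.3.2, was read for the asterisk.

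| Unsolicited event | By-arm total (117) | By-term count (130) | By-term listing (134–138) |
|---|---|---|---|
| Non-serious, related | yes | yes | if moderate or severe, or AESI, PIMMC or NOCMC |
| Non-serious, unrelated, moderate or severe | yes | no | yes (138) |
| Serious, any relationship | yes, under serious AEs | no | yes (134) |
| Mild, non-serious, unrelated, AESI, PIMMC or NOCMC | yes | no | yes (135–137) |
| Mild, non-serious, unrelated, none of these | yes | no | no |

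Only the last row is invisible by term. Tables 134 to 138 are listings without counts or denominators, so a by-arm comparison by term has to be tallied by hand across six arms.

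**2. The plan's own detection figure.** Protocol Table 10 (SAP Table 3) gives the chance of seeing at least one event in an arm of 40 as 98% for 10% frequency and 33% for 1%. From 1 − (1 − p)^n: 1 − 0.9^40 = 98.5% and 1 − 0.99^40 = 33.1%. Both reproduce, the first after truncation.

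**3. Share of events visible by term.** Let r be the share judged related and m the share that are mild, with relationship and severity independent of each other and of arm, and the term outside Tables 134 to 137. The share visible in Tables 130 and 138 together is v = r + (1 − r)(1 − m). The documents give neither r nor m, so both are assumed.

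- r = 0.5, m = 0.5: v = 0.5 + 0.5 × 0.5 = 0.75.
- r = 0.25, m = 0.5: v = 0.25 + 0.75 × 0.5 = 0.625.

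The invisible share is (1 − r)m. It runs from 0.25 × 0.5 = 12.5% (r = 0.75, m = 0.5) to 0.9 × 0.9 = 81% (r = 0.1, m = 0.9).

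**4. Effect on seeing an imbalance.** Take one term with true incidence 30% v 5% and 40 subjects per arm (Protocol 11.4.2). Multiply both rates by the visible share and enumerate all outcomes of a two-sided Fisher's exact test at 0.05.

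| Events counted | Rates | Expected counts | Power |
|---|---|---|---|
| All (Table 129) | 30% v 5% | 12 v 2 | 82% |
| 130 and 138, r = 0.5, m = 0.5 | 22.5% v 3.75% | 9 v 1.5 | 62% |
| 130 and 138, r = 0.25, m = 0.5 | 18.75% v 3.125% | 7.5 v 1.25 | 48% |
| 130 alone, r = 0.5 | 15% v 2.5% | 6 v 1 | 32% |
| 130 alone, r = 0.25 | 7.5% v 1.25% | 3 v 0.5 | 5% |

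The plan specifies no such test. Power here only measures how visible an imbalance would be.

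**The case against.** The case for leaving the marking alone is substantial, and it rules out several stronger readings.

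- A reader might infer that the DSMB sees this primary outcome only through a causality filter. It does not: Table 117 shows any unsolicited AE by arm, unfiltered.
- A reader might infer that unrelated events are absent by term and arm. They are not: the listing shells carry arm, relationship, SOC and preferred term. Tables 135 to 137 have no severity or relationship filter, so even some mild, unrelated events appear there. Medically attended events may be among them, since the protocol groups these with AESIs and the Table 135 shell has a column for them, although the SAP does not settle this.
- A reader might take 32% and 5% as the loss. Those figures ignore Table 138.
- A reader might say that the filter removes most events. No related share is given, and Protocol 9.2.1 tells physicians always to suspect the study product.

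The consequences are also limited. The report follows the last Day 57 visit, so all adjuvanted doses have been given; the Day 90 vaccine has no adjuvant. Protocol 11.5 and SAP 6.2.1 say that the report's analyses will not drive decisions on trial conduct. The manufacturer of AF03 and both vaccines receives the unblinded data set itself. The DSMB has an earlier review at 50% of subjects, may request more data, and works under a charter that is not among the documents, so other DSMB tables cannot be excluded.

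All of this stands, and it narrows the point without removing it. One overall row cannot show which term is out of balance, and background events can dilute an excess in a single term. A hand-tallied listing without mild events is a weak substitute for a count with a denominator. A board that sees no signal has no evident reason to ask for the missing table.

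**Conclusion.** The point holds in a limited form. Table 130 is the only marked frequency table of unsolicited AEs by SOC, preferred term and arm, and it is restricted to non-serious related events, although the primary outcome has no such restriction. The gap is the absence of an all-causality count by term and arm. The events lost at term level are those that are mild, non-serious, judged unrelated and outside Tables 134 to 137.

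The size cannot be fixed from the documents. In the illustration, power falls from 82% to between 62% and 48%, given the assumed incidences and shares, independence of relationship and severity, and a reader who tallies Table 138 correctly. The gain from closing the gap is better DSMB oversight during follow-up and better information for later trials. It cannot protect subjects at the first vaccination. The full tables remain planned for the clinical study report.

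**What to change.** Add the asterisk to Table 129 in the list of tables and in its shell, so that all unsolicited AEs from Day 1 to Day 29 appear in the expedited report by SOC, preferred term, severity, relationship and arm. Table 127, which gives confidence intervals, would also serve. Keep Table 130 as the related-only subset.

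The table is already specified, and its data fall within the database locked after Day 57, so no new collection or method is needed. The cost is a longer report.
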